#### **6.3.4.2 Determine MTD or RP2D**

The MTD is defined as the dose at which 0/6 or 1/6 subjects in the current dose group experience a DLT, provided that  $\geq 33\%$  of subjects experience a DLT at the next higher dose (i.e., 2/3 or 2/6). Even if the MTD has been reached, the selection of the RP2D still requires reference to the MTD and the following available information: low-grade AEs, AEs occurring in subsequent treatment cycles, PK and efficacy data. In the dose escalation phase, if the MTD cannot be determined based on the planned dose (e.g., further dose escalation does not result in a significant increase in exposure), the RP2D will evaluate the available safety, PK, and efficacy data via a dose escalation teleconference or teleconference to determine the dose for the dose expansion phase.

Once the MTD has been determined through a safety assessment meeting, additional approximately 3 subjects may be enrolled at the previous low dose level to collect additional PK and safety data upon discussion between the sponsor and the site. At least 6 subjects will be treated at the MTD/RP2D. The MTD/RP2D was selected as the dose for further study in Part Ib.

#### **6.3.5 SMC Responsibilities**

The Safety Monitoring Committee (SMC) will be responsible for safety supervision, dose escalation design, determination of MTD or RP2D, and other important study decisions. However, in case of disagreement between the trial sponsor and the SMC, the decision process will be described in the SMC Charter.

#### **6.4 Evaluation of Kinetics**

In the clinical study, the concentrations of three drug components of MRG003 in the systemic circulation of subjects, total antibody, conjugated antibody and unconjugated drug, as well as anti-drug antibody, will be detected. Before, during and after intravenous drip of MRG003, blood samples will be collected from all subjects at set time points, and PK parameters (not limited to  $C_{max}$ ,  $T_{max}$ ,  $t_{1/2}$ , MRT,  $V_d$ , CL,  $AUC_{0-t}$  and  $AUC_{0-inf}$ , etc.) of the above components in serum will be analyzed.

Refer to Table 7 for PK and ADA serum sample collection points. Blood samples will be collected from vein during blood collection. The test items, blood volume and treatment are shown in Table 8. The blood collection time should be recorded in detail in the eCRF

to minute. If other blood collection time points coincide with PK blood collection time points, PK blood collection should be performed first.

# **6.5 Efficacy Assessments**

Response to tumor therapy will be assessed in this study using Response Evaluation Criteria in Solid Tumors RECIST v1.1, see Appendix II.

The primary outcome measure of Ib trial is objective response rate (ORR), the proportion of subjects with confirmed overall CR and confirmed overall PR in all subjects who have received the study drug.

Progression-free survival (PFS) for this study is defined as the time from the start of treatment with MRG003 until objective tumor progression or death from any cause. Duration of response (DOR) is defined as the time from the first documented response until disease progression or death among subjects with a confirmed objective response (CR or PR), with tumor evaluation according to RECIST v1.1 criteria. Overall survival (OS) is defined as the time from the start of treatment with MRG003 to death due to any cause.

For patients without disease progression after the last dosing cycle, tumor response should be assessed every 6 weeks and followed up for survival until disease progression or other anti-tumor treatment. Survival follow-up could be performed every 12 weeks after confirmation of disease progression or receipt of additional antineoplastic therapy. The follow-up period starts from the end of treatment cycle until death or study termination. During follow-up, survival status and subsequent tumor treatment need to be examined and recorded. Subsequent tumor treatment does not need to be recorded in electronic case report form (eCRF).

Tumor evaluation will be performed according to RECIST v1.1, and the results of imaging assessment methods should be recorded in the electronic case report form. During trial treatment, radiographic assessments may be performed  $\pm$  7 days from the scheduled date and the methodology should be consistent between baseline and subsequent follow-up. Whenever clinically permissible, the same oral or intravenous contrast agent was used for each scan, and, whenever possible, the same investigator/radiologist evaluated all patient scans during the study.

# 7 TRIAL, WITHDRAWAL, DISCONTINUATION

# 7.1 Number of subjects

Part Ia: Approximately 26 patients with solid tumors will participate in the dose escalation study to determine MTD/RP2D;

Part Ib: 36 evaluable patients with advanced colorectal cancer, 12 patients with head and neck squamous cell carcinoma and 12 patients with nasopharyngeal carcinoma.

# 7.2 Study site

693

698

- 694 Part Ia: Single center: Sun Yat-sen University Cancer Center
- 695 Part Ib: Multicenter: The leading site of the study is Sun Yat-sen University Cancer
- Center in Guangzhou. An additional 4-8 additional sites will be selected based on the 696
- 697 progress of the trial.

#### 7.3 Inclusion criteria

- 699 Gender: Male or female;
- 700 2) Age:  $\geq 18$  years,  $\leq 75$  years;
- 701 Life expectancy  $\geq 12$  weeks;
- 702 Phase Ia dose escalation phase: patients with histologically or cytologically confirmed
- 703 locally advanced or metastatic solid tumors who have failed or cannot obtain standard
- treatment; 704
- 705 Phase Ib dose expansion phase: patients with histologically or cytologically confirmed
- 706 locally advanced or metastatic colorectal cancer, head and neck squamous cell
- 707 carcinoma or nasopharyngeal carcinoma, who have failed standard treatment, cannot
- tolerate standard treatment or cannot obtain standard treatment; 708
- 709 For patients participating in phase Ib clinical trial, their pathological samples shall be
- positive for EGFR expression by immunohistochemical detection; 710
- 711 Patients must have at least one measurable lesion as defined by RECIST v1.1;
- 712 ECOG score of 0-1;
- 713 Patient has organ function meeting the following laboratory test results at baseline
- 714 examination at the time of enrollment:
- 715 Blood function
- 716 Absolute neutrophil count  $\geq 1.5 \times 109/L$ ;
- 717 Platelets  $\geq 100 \times 109/L$ ;
- 718 Hemoglobin  $\geq 9 \text{ g/dL}$ ;
- Hepatic and renal function: 719
- 720 Total bilirubin  $\leq 1.5 \times \text{upper limit of normal (ULN)};$
- 721  $ALP \le 1.5$  times ULN. If the patient has bone metastasis, ALP has no upper
- 722 limit;

- AST and ALT: ≤ 2.5 times ULN for patients without liver metastasis or ≤ 3
   times ULN for patients with liver metastasis;
- International normalized ratio < 1.5 times ULN (anticoagulant naïve) or international normalized ratio < 3 times ULN (anticoagulant naïve);
- Serum creatinine ≤ 1.5 times ULN;
- 728 10) Women of childbearing age must have a negative serum pregnancy test before 729 entering this study and agree to take complete contraception from the beginning of the 730 study to at least 6 months after administration of the study drug; female patients 731 without childbearing potential should have spontaneous amenorrhea for at least 12 732 months; or have undergone oophorectomy, hysterectomy or tubal ligation more than 6 733 weeks before screening; in the case of unilateral oophorectomy, their fertility status 734 will be determined by hormone levels;
- Male patients must agree to use effective contraceptive measures (male condom with spermicide, or provide evidence of successful vasectomy; an intrauterine device with spermicide, female condom with spermicide, contraceptive sponge with spermicide, intravaginal contraceptive, diaphragm with spermicide, cervical cap with spermicide, or oral/implanted/or injectable contraceptives) from the start of the study to at least 6 months after study drug administration;
- 741 12) Patients voluntarily signed the written informed consent form to participate in this clinical trial, followed the study schedule and other requirements of the protocol.

#### 7.4 Exclusion Criteria

743

755

756757

- Any subject who had any of the following conditions was excluded from the study
- 745 1) History of allergic reaction to any component of MRG003;
- Patients with symptomatic central nervous system (CNS) metastases;
- 747 Note: patients with a previous history of central nervous system metastases who 748 have completed treatment can participate in this trial, that is, patients who have 749 completed treatment for CNS metastases after radiotherapy or surgery 2 weeks before participating in this study and are neurologically stable (no new 750 neurological deficits caused by brain metastases are found in clinical screening 751 and no new lesions are found in central nervous system imaging) can participate 752 753 in this study. If the patient requires steroids for treatment of CNS metastases, 754 steroids must have been discontinued 2 weeks prior to the first dose;
  - 3) Patients with a history of other primary malignancies, (except locally resected skin cancer and carcinoma in situ of the cervix, but melanoma needs to be excluded). Patients who previously suffered from other primary tumors but were

- 758 able to provide treatment for more than 3 years without tumor recurrence or 759 progression can participate in this study; 760 4) Patients with a history of clinically significant liver disease, such as hepatitis C (positive hepatitis C antibody test) or chronic active hepatitis B (positive HBsAg 761 for more than 6 months, HBV DNA  $\geq$  2000 IU/ml, ALT  $\geq$  2 ULN and excluding 762 763 hepatitis caused by drugs or other reasons), alcoholic hepatitis, non-alcoholic steatohepatitis, hepatectomy, cirrhosis, etc.; 764 765 5) Patients with known human immunodeficiency virus (HIV) infection; 766 History of the following ophthalmologic abnormalities, e.g.: 767 Severe dry eye syndrome; 768 Keratoconjunctivitis sicca; 769 Severe exposure keratitis; Any other condition that may result in an increased risk of corneal epithelial 770 771 damage; 772 7) Patient has any serious and/or uncontrolled disease or other condition that, in the opinion of the Investigator and Sponsor, may compromise the patient's 773 774 participation in this study, as follows: 775 Uncontrolled diseases, or participation in this study may affect the control 776 of these diseases; 777 History of interstitial pneumonia, radiation pneumonitis, severe chronic 778 pulmonary severe pulmonary obstructive disease. insufficiency, symptomatic bronchospasm; 779 780 Life-threatening autoimmune diseases and ischemic diseases; 781 8) Patients with impaired cardiac function or clinically significant cardiac disease, including any of the following: 782 783 Heart rate-corrected baseline QT interval calculated by Fridericia's formula > 450 msec, or congenital QT prolongation syndrome; 784 785 Concomitant diseases that may prolong QT interval as assessed by the
- History of severe uncontrolled arrhythmia;

heart failure:

786

787

788

investigator, such as autonomic neuropathy (due to diabetes or Parkinson's

disease), HIV infection, liver cirrhosis, uncontrolled hypothyroidism, or

- Patients having: myocardial infarction, unstable angina pectoris, coronary artery bypass grafting, congestive heart failure, cerebrovascular accident or transient ischemic attack within 3 months prior to the first dose;
  - 9) Use of chemotherapy, biological therapy, immunotherapy, radiotherapy, other clinical studies and other anti-tumor treatment within 4 weeks prior to the first dose; or have not recovered from side effects of the above treatment (CTCAE v4.03 grade 2 or higher). If the half-life of the antineoplastic drug used by the patient is very short (such as fluorouracil), this patient can be appropriately relaxed, which may be allowed to take the drug 2 weeks later. However, this individual case needs to be communicated with and agreed by the sponsor;
  - 10) 4. Major surgery or surgical treatment for any reason before the first dose;
- 11) The patient has a planned surgery during the study period, or the investigator considers the patient requires surgery;
  - 12) History of severe skin diseases requiring interruption of previous EGFR-targeted therapy; or chronic skin diseases requiring oral or intravenous therapy as prescribed;
    - 13) The patient has any other concomitant disease that may increase the risk of toxicity as considered by the investigator or sponsor;
  - 14) Pregnant or lactating.

#### 7.5 Subject Withdrawal Criteria

#### 7.5.1 Investigator's decision to withdraw a subject

Withdrawal of a subject from the trial refers to that the enrolled subject suffers from conditions unsuitable for continuation of the trial during the trial. The investigator decides to withdraw the subject from the trial, and the investigator decides to withdraw the subject from the trial for diagnosis and treatment measures.

- 815 (1) Unequivocal disease progression;
- 816 (2) Subject died;

793

794

795

796 797

798

799

800

803

804

805

806

807

808

809

810

811

812

813

814

- The subjects with adverse events and serious adverse events who are not suitable for continuation of the trial as judged by the investigator should continue to be followed up for 21 days or until the adverse reactions are relieved or recovered;
- Use of other therapies or drugs that affect the efficacy and safety judgment;
- Patients with poor medication compliance who cannot make a visit on time during two consecutive visit time windows.

# 7.5.2 Withdrawal by subject

823

824

825

826 827

828

829830

831

832

833

834

835

836

837

838

839 840

841

855

According to the Good Clinical Practice (GCP), subjects have the right to withdraw from the study at any time for any reason, or they are lost to follow-up due to failure to observe and test the investigational drug but do not explicitly propose to withdraw from the study, which also belongs to "withdrawal" or "dropout". For subjects withdrawing from the trial, the reason for withdrawal should be known as much as possible and recorded in the eCRF. Possible reasons: withdrawal of the ICF; perceived poor efficacy; intolerance to some adverse reactions; inability to continue the clinical study due to work or life effects; loss to follow-up due to economic factors or unexplained reasons.

Regardless of the reasons, for the subjects who withdraw from the trial, the records of their last subject visit/follow-up cases (including laboratory tests and test indicators) should be retained, and the efficacy and adverse reactions should be analyzed in the full data set by taking them as the last test results and transferring them into the final results.

#### 7.6 Criteria for Discontinuation

Trial suspension refers to stopping the trial halfway when the clinical trial has not been completed as per the protocol. The purpose of trial suspension is to protect the rights and interests of the subjects, ensure the quality of the trial and avoid unnecessary economic losses. The investigator should carefully document the reason for discontinuation. Criteria for discontinuation:

- Multiple serious adverse events occurred in the study, which affected the investigators' judgment on the safety of the investigational drug;
- The study found that the clinical trial protocol had major defects, making it difficult to evaluate the drug effect, especially affecting the safety and health of subjects;
- 846 (3) The investigators are found to have serious deviations in the implementation of 847 study protocol and standard operating procedures (SOPs) during the 848 implementation of the study, which cannot achieve the purpose of study evaluation;
- Significant management defects of the study or risks of the study are found in the IEC follow-up ethics review process, which require suspension of the ongoing study;
- The sponsor requests suspension (e.g., economic reasons, administrative reasons and/or the study effect fails to achieve the expected results);
- 854 (6) China Food and Drug Administration ordered to terminate the trial for some reason.

#### 7.7 Exclusion criteria

856 (1) Accidental case;

- 857 (2) Those who meet the inclusion criteria and have not taken the drug after inclusion;
- The combination of drugs beyond the specified range, especially the combination of drugs, has a great impact on the evaluation of trial results and affects the efficacy and safety judgment;
- 861 (4) Participating in other clinical trials during the trial;

The reasons for exclusion should be explained, and the eCRF should be retained for future reference. The excluded cases were not included in the statistical analysis of efficacy; however, the excluded cases who had received the study drug treatment and had safety records could be included in the safety analysis as appropriate.

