#### 10.3 Permitted concomitant medications and treatments

Due to the unique nature of oncology patients, subjects were allowed to receive adequate supportive care during the study as medically necessary and documented in the eCRF.

- 1) During the trial treatment, when the study drug causes acute toxic reactions, such as febrile neutropenia, the investigators should decide to give the subjects biological response modifiers (BRMs), such as G-CSF or GM-CSF, in combination with other concomitant symptoms and risk factors of clinical patients. The specific protocol can follow the clinical medication routine of each hospital; however, the use of biological response modifiers for patients to meet the trial inclusion criteria is not allowed, and the use of prophylactic biological response modifiers during the first dosing cycle is not allowed.
- 2) Prophylactic anti-allergic treatment, preventive antiemetic treatment;
- 3) Therapeutic use of antibiotics, e.g., in case of febrile neutropenia or infection;
- 4) In case of diarrhea, antidiarrheal treatment should be performed according to the routine of the hospital;

- Palliative radiotherapy for analgesic purposes may be given (if bone metastases occur) to control pain. The irradiated area should be as small as possible. No target tumor lesion should be included in the irradiated area, otherwise the patient will be excluded from the trial, and the patient will not participate in the evaluation of tumor response. Radiation area can not be used as the parameter for response evaluation;
  - 6) Other symptomatic treatment for drug toxicity may be given at the discretion of the investigator based on the specific condition of the subject and should be recorded in detail in the eCRF.

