#### 14.3 Data Analysis Set

Safety Set (SS): includes all subjects who received at least one treatment. Safety analysis set is used for safety analysis and primary analysis of efficacy indicators.

Evaluable Analysis Set: Phase Ia includes subjects who have at least one post-treatment tumor assessment; Phase Ib includes subjects who have not achieved CR and PR response and have at least one evaluable baseline post-treatment tumor assessment, and subjects who have achieved CR and PR response include at least two post-treatment tumor assessments (and are at least 4 weeks apart). The evaluable analysis set was used for secondary analyses of efficacy measures.

PK Analysis Set (PKS): includes subjects who received at least one treatment and had at least one valid post-treatment PK concentration measurement. The PK analysis set was used for the analysis of PK parameters.

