#### 14.4.3.2 Primary Outcome Measures in Part Ib

According to RECIST v1.1, evaluate the treatment indicators related to tumor measurement: objective response rate (ORR = 100% x (CR + PR)/total number of subjects in analysis set), and calculate the corresponding 95% CI.

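### Section 7.7 takes some treated subjects out of the efficacy analysis, contradicting the all-treated denominator that 6.5 and 14.3 set for the Phase Ib primary ORR

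*Protocol*

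**What the plan says.** **Primary denominator.** Protocol 6.5 defines the Phase Ib primary ORR as "the proportion of subjects with confirmed overall CR and confirmed overall PR in all subjects who have received the study drug". Section 14.3 agrees. The Safety Set "includes all subjects who received at least one treatment", and "Safety analysis set is used for safety analysis and primary analysis of efficacy indicators". A narrower set has its own place: "The evaluable analysis set was used for secondary analyses of efficacy measures". The formula in 14.4.3.2 divides by the "total number of subjects in analysis set", with a 95% CI.

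**Exclusions.** Section 7.7 lists four grounds: accidental cases (item 1), subjects never dosed (item 2), "The combination of drugs beyond the specified range" (item 3) and taking part in another trial (item 4). It then states: "The excluded cases were not included in the statistical analysis of efficacy". It recognises that some of these subjects will have been treated, and leaves their inclusion in the safety analysis to discretion.

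**Related text.** Section 10.3(5) requires that palliative radiotherapy cover no target lesion, "otherwise the patient will be excluded from the trial, and the patient will not participate in the evaluation of tumor response". Section 7.5.1 lists use of other therapies that affect the efficacy judgement as a reason for withdrawal. Section 7.5.2 says that, whatever the reason, the last results of withdrawn subjects are analysed in the full data set. Section 7.8 carries a drop-out's last primary efficacy result into the final analysis.

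**The concern.** A single-arm ORR depends directly on who is counted. Under 6.5 and 14.3, a treated subject without a confirmed response stays in the denominator. Under 7.7, the same subject leaves it after taking a disallowed drug or joining another trial. Both events can occur after treatment has started, and both are plausible in a patient whose disease is not responding. The denominator would then depend partly on outcome. The trial is open-label, so results are visible when someone decides whether a subject counts as excluded.

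The protocol intends this trial to supply preliminary efficacy results for Phase II (6.1). With about 12 subjects per tumour type, one or two deletions visibly move the estimate.

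**Working it through.** **1. The plan's own figure.** Section 14.1 gives 36 Phase Ib subjects, 12 per tumour type: 3 × 12 = 36, which agrees. There is no power calculation or target rate to reproduce.

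**2. Each ground against the all-treated denominator.**

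| Rule | Can the subject have been treated? | Conflict with 6.5 and 14.3? |
|---|---|---|
| 7.7(1) accidental case | Not defined | Cannot be judged |
| 7.7(2) never dosed | No | None; already outside the set |
| 7.7(3) disallowed drugs | Yes | Yes |
| 7.7(4) another trial | Yes | Yes |
| 10.3(5) target lesion irradiated | Yes | Ambiguous; see below |

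The sentence in 7.7 is not limited to the Evaluable Set, and no section ranks the rules. Items 3 and 4 therefore contradict 6.5 and 14.3. Item 3 also sits badly with 7.5.1 and 7.5.2, where use of other therapies leads to withdrawal with the efficacy data kept.

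Section 10.3(5) names no denominator. It can mean that the subject leaves the ORR, or only that response is no longer assessed. In the second case the subject can stay in the denominator under the non-evaluable (NE) category of 14.4.4.2.

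**3. Size.** Responder and removal counts are assumptions; the protocol gives none. ORR = x/n, with x confirmed responders among n subjects counted, and exact (Clopper-Pearson) 95% CIs. With 12 treated and x = 3:

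| Removed | ORR | 95% CI |
|---|---|---|
| none | 3/12 = 25.0% | 5.5 to 57.2 |
| 1 non-responder | 3/11 = 27.3% | 6.0 to 61.0 |
| 2 non-responders | 3/10 = 30.0% | 6.7 to 65.2 |
| 3 non-responders | 3/9 = 33.3% | 7.5 to 70.1 |
| 1 responder | 2/11 = 18.2% | 2.3 to 51.8 |

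For any x, removing k non-responders multiplies the ORR by 12/(12 − k): 12/11 = 1.09, 12/10 = 1.20, 12/9 = 1.33. With two removed, 2 responders go from 16.7% to 20.0%, 4 from 33.3% to 40.0%, and 5 from 41.7% to 50.0%.

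Over all 36 with 9 responders, removing 1, 2 or 3 non-responders moves 25.0% to 9/35 = 25.7%, 9/34 = 26.5% or 9/33 = 27.3%.

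**4. Alternative base.** The protocol plans 12 evaluable subjects per tumour type, so removed subjects might come on top of the 12. The 7.7 figure is then 3/12 = 25.0%, against all-treated figures of 3/13 = 23.1%, 3/14 = 21.4% or 3/15 = 20.0%. The direction is the same and the gap is smaller.

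**The case against.** **Direction.** A reader might infer that 7.7 certainly inflates the ORR. The documents do not support that. Many failing patients are handled elsewhere: progression ends treatment (9.8, 10.4) and leads to survival follow-up (9.7) with progression already recorded, and 7.5.2 and 7.8 retain the results of withdrawn subjects and drop-outs. Item 3 could also remove an apparent responder whose response is confounded by another drug, which lowers the ORR. This stands, so direction is a likelihood. An upward route remains, however. Read literally, item 4 also catches a patient who progresses and joins another trial during survival follow-up, and that patient is a non-responder in the all-treated analysis.

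**Radiotherapy.** A reader might treat 10.3(5) as a second flat contradiction. It states no denominator and is compatible with NE status, so it needs clarifying but does not carry the finding.

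**Safety.** A reader might infer that adverse event rates become discretionary. Sections 14.3 and 14.4.5 base safety firmly on all treated subjects, and section 11 evaluates toxicity in everyone infused. The discretion in 7.7 is loose wording against these statements.

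**Importance.** Phase Ib is exploratory, has no formal sample-size calculation and ties no ORR threshold to a decision. The shifts are small beside the intervals. This lowers the severity, but wide intervals do not justify two definitions of the only Phase Ib primary endpoint.

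**The unseen SAP.** A SAP could choose one denominator, but the conflicting protocol text would remain. Section 14.2 requires both documents to be amended when the analysis methods for primary objectives change.

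**Conclusion.** The contradiction holds for 7.7(3) and 7.7(4) against 6.5 and 14.3. Item 2 does not conflict, item 1 is undefined, and 10.3(5) is ambiguous. The 7.7 denominator may bias the ORR, most likely upward. In a cohort of 12 treated, each non-responder removed adds roughly 2 to 3 percentage points if there are 3 responders; removing a responder moves the estimate down by about 7 points (25.0% to 18.2%). These sizes rest entirely on assumed counts and on taking 12 as the number treated. The textual conflict does not depend on them. It should be fixed, but does not undermine the trial.

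**What to change.** - **7.7:** State that every subject who received at least one dose stays in the Safety Set for the primary ORR and all safety tables. A subject without a confirmed CR or PR before the event counts as not having responded, and is reported as NE where applicable. Apply the 7.7 exclusions only to the secondary Evaluable Set analysis or a sensitivity analysis. Define or delete item 1, and remove the discretion over safety inclusion.
- **10.3(5):** Clarify that assessments after irradiation of a target lesion are not used for response, and that the subject remains in the primary ORR denominator. The radiotherapy and withdrawal provisions themselves stay unchanged.
- **7.5.2 and 7.8:** Align the last-result rules with the above, so that no competing rule for the same endpoint remains.

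The cost is protocol wording only, with no extra subjects or visits. The reported ORR may be slightly less favourable. Counting these subjects as not having responded is a choice of handling rule, but it follows directly from the all-treated definition already in 6.5.
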